5.2 Trial Analysis Sets

The trial analysis sets are defined in [Table 2](#). The analysis sets are described in more detail in the Analysis Set Definition Document.

Table 2: Trial analysis sets

Analysis set	Definition
Enrolled subjects	All subjects enrolled (informed consent obtained) in the trial.
Open-label safety analysis set	All subjects exposed to LEO 90100 during the open-label phase.
Open-label HPA analysis set	All subjects in the open-label safety analysis set who provided consent for the Adrenocorticotrophic Hormone (ACTH) challenge test and underwent a Hypothalamic-Pituitary-Adrenal (HPA) axis test.
Full analysis set	All subjects randomised who had treatment success at randomisation, defined as PGA score of 'clear' or 'almost clear' with at least a 2-grade improvement from baseline. Subjects randomised without treatment success will be excluded from the full analysis set. This approach is in alignment with the ICH E9, since achieving treatment success is a major randomisation criterion measured prior to randomisation and therefore exclusion of such subjects will not introduce bias.
Per protocol analysis set	The per protocol analysis set will be defined by excluding subjects from the full analysis set as described in the protocol and in the Analysis Set Definition Document.
Safety analysis	All subjects exposed to IMPs following randomisation and with available

set	post-randomisation safety evaluations.
Randomised subjects	All subjects randomised to the maintenance phase.
HPA analysis set	All subjects in the safety analysis set who provided consent for the ACTH challenge test and underwent an HPA axis test.

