13. At Visit 1, a normal HPA axis function including a serum cortisol concentration above 5 mcg/dl before ACTH-challenge and above 18 mcg/dl 30 minutes after ACTH-challenge.

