The ACTH-challenge test will be performed at baseline (Visit 1), after 4 weeks (Visit 2), after 28 weeks (Visit 8) and at the end of trial (Visit 15 or at early withdrawal). If the subject withdraws prior to completing the initial open-label treatment phase, the ACTH-challenge test scheduled for Visit 2 should not be performed. If the subject discontinues the trial prior to week 56 (this also includes discontinuation due to not achieving 'clear' or 'almost clear' disease status following 4 weeks of once daily treatment following a relapse in psoriasis status), a follow-up visit must be scheduled within 7 days of the last treatment period visit for the purpose of performing the ACTH-challenge test, if the test was not performed on the same day (rescheduling required due to the time dependency of the ACTH-challenge test).

Subjects will not be included in this procedure of the trial if one of the following applies to the serum cortisol concentration at Visit 1:

- ≤ 5 mcg/dl pre-stimulation (before CORTROSYN® / Synacthen® injection)
- ≤ 18 mcg/dl at 30 minutes after CORTROSYN® / Synacthen® injection

If the ACTH challenge test at Visit 15 (end of maintenance phase) or at early withdrawal shows a serum cortisol concentration ≤ 18 mcg/dl at both 30 minutes and 60 minutes after the ACTH challenge, a further ACTH-challenge test is required 4 weeks later (FU2 visit).

If the results of the ACTH-challenge test at the FU2 visit continue to show a serum cortisol concentration ≤ 18 mcg/dl at both 30 minutes and 60 minutes after ACTH challenge, further ACTH challenge tests should be performed, but not more often than at 4-weekly intervals, until the adrenal suppression resolves (i.e. serum cortisol concentration > 18 mcg/dl at 30 minutes or at 60 minutes after the ACTH challenge, or at both time-points). The data from such further ACTH challenge tests must be captured in the unscheduled follow-up visit page in the eCRF.

The following procedures should be performed prior to the ACTH challenge tests: Heart rate and blood pressure, blood/urine sampling for central laboratory analysis (biochemistry/urinalysis), blood sampling for biomarkers and urine pregnancy test (in female subjects of child-bearing potential).

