5.1 Definition of trial periods

The trial periods are defined in [Table 1](#).

Table 1: Definition of trial periods

Trial period	Definition
Open-label phase	From the day of enrolment to the day before randomisation.
Randomised phase	From the day of randomisation to end of trial, both days included.
Maintenance phase	From the day of first exposure to maintenance IMP to the last day of exposure (rescue or maintenance IMP), both days included.
Follow-up phase	From the day after last application of maintenance or rescue IMP to end of trial.
Relapse period	Relapse is defined as a PGA score of at least 'mild' during the maintenance phase, for details on relapse see CTP section 6.14.1. A relapse period is defined from the relapse start day (included) to the

	visit date when relapse treatment is discontinued (not included).
Remission period	A remission period is a period where the subject is not in a relapse period within the maintenance phase.
Visit interval	The interval between two successive scheduled visits.

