Figure 3-1 Mean plot of serum-cortisol concentration at time 0, and at 30 and 60 minutes after ACTH-challenge test for visit 1 and visit 2; open-label HPA analysis set

Figure 3-2 Mean plot of serum-cortisol concentration at time 0, and at 30 and 60 minutes after ACTH-challenge test by treatment for visit 2, visit 8 and visit 15; HPA analysis set

Patient Data Listings (Appendix 1)

1-6 Randomisation

1-7 Subjects receiving Investigational Product from Specific Batches

Patient Data Listings (Appendix 2)

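### The open-label HPA analysis set does not apply inclusion criterion 13, so the Visit 1 and Visit 2 cortisol means can rest on different subjects

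*SAP*

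**What the plan says.** Protocol 7.2, criterion 13, asks subjects in the HPA part for "a normal HPA axis function including a serum cortisol concentration above 5 mcg/dl before ACTH-challenge and above 18 mcg/dl 30 minutes" after the challenge, judged at Visit 1. Protocol 8.12.1 states what follows from a low result: "Subjects will not be included in this procedure of the trial if one of the following applies to the serum cortisol concentration at Visit 1", the limits being 5 mcg/dl or less before stimulation and 18 mcg/dl or less at 30 minutes.

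SAP 5.2, Table 2, defines the open-label safety set as "All subjects exposed to LEO 90100 during the open-label phase". The open-label HPA set adds two conditions, consent and having had an HPA axis test. The maintenance HPA set puts the same conditions on the safety analysis set: "who provided consent for the ACTH challenge test and underwent an HPA axis test". Neither definition refers to criterion 13. The section adds: "The analysis sets are described in more detail in the Analysis Set Definition Document". That document was not available for this review.

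SAP 5.5.7 summarises cortisol at 0, 30 and 60 minutes at Visits 1 and 2 for the open-label phase. Shell 94 gives the means by visit, and Figure 3-1 plots them "after ACTH-challenge test for visit 1 and visit 2; open-label HPA analysis set". The maintenance outputs (Shells 97 and 98, Figure 3-2) cover Visits 2, 8 and 15.

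**The concern.** The test that decides criterion 13 is the same test that admits a subject to the HPA set. Anyone who fails on cortisol has already consented and been tested, so both conditions in Table 2 are met at the moment the subject becomes ineligible for further ACTH testing. Such a subject contributes to the Visit 1 mean and cannot contribute to the Visit 2 mean.

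The HPA effect is a listed safety assessment (protocol 5.3). The open-label summary is the only planned output that sets cortisol before any LEO 90100 beside cortisol after it, and there is no control arm in that phase. A change in who is averaged cannot be separated from a drug effect by looking at the two means. The direction is also the unhelpful one for safety, because losing low responders lifts the second mean relative to the first.

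**Working it through.** The plan states no figure on this point, so there is none to reproduce. The check has two parts.

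**Tracing one criterion-13 failure through the text**

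1. The subject consents and has the Visit 1 ACTH test, so the consent and test conditions of Table 2 are met.
2. Protocol 6.1.3 puts the first application on the day of Visit 1, and 8.12.1 has cortisol measured at the Central Laboratory. A result arriving after the first dose is an inference, since no turnaround time is given. Even if the result came first, criterion 13 is an additional criterion for the HPA part, and 8.12.1 removes the subject from that procedure, not from the trial. Exposure, and so the open-label safety set, can follow.
3. Under 8.12.1 there is no ACTH test at Visit 2, 8 or 15.
4. Result: a member of the open-label HPA set with a Visit 1 value only. If later randomised and treated, the subject is also in the maintenance HPA set, with no cortisol value at any visit shown there.

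**Sizing the shift (illustration)**

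Inputs from protocol 11.1: an aim of about 25 HPA subjects with 52 weeks of exposure, 30% drop-out over 52 weeks with exponential decline, and 48% open-label success. As a check on the drop-out input, 380 × 0.7^(22/52) = 326.8 and 380 × 0.7^(48/52) = 273.4, against the stated 326 and 273.

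- Randomised HPA subjects needed: 25 / 0.7^(48/52) = 25 / 0.7195 = 34.7, about 35.
- Open-label HPA subjects needed: 34.7 / 0.48 = 72.4, about 72. This applies the whole-trial success rate to the HPA part.

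Let N be the eligible subjects, k the retained failures on the 30-minute limit, f = k/(N+k), and d the gap in mean 30-minute cortisol between eligible subjects and failures. The values of k and d are assumptions: k = 1 to 5, d = 10 mcg/dl. N = 72 follows from the scaling above, and N = 35 is used as a smaller group. The Visit 1 share at or below 18 mcg/dl is f, against 0 by construction if criterion 13 were applied. The Visit 1 mean is lowered by d × f.

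| N | k | f | d × f (mcg/dl) |
|---|---|---|---|
| 72 | 1 | 1/73 = 1.4% | 0.14 |
| 72 | 3 | 3/75 = 4.0% | 0.40 |
| 72 | 5 | 5/77 = 6.5% | 0.65 |
| 35 | 1 | 1/36 = 2.8% | 0.28 |
| 35 | 3 | 3/38 = 7.9% | 0.79 |
| 35 | 5 | 5/40 = 12.5% | 1.25 |

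These shifts are upper limits, because selection on a high Visit 1 value brings regression to the mean. Suppose there is no drug effect, the mean and spread are the same at both visits, and the between-visit correlation is ρ. If M is the eligible subjects' Visit 1 mean, the mean of everyone tested is M − df, and the eligible subjects' expected Visit 2 mean is (M − df) + ρdf = M − (1 − ρ)df. Then:

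- Unpaired, as planned: [M − (1 − ρ)df] − [M − df] = +ρdf, an apparent rise.
- Eligible subjects at both visits: [M − (1 − ρ)df] − M = −(1 − ρ)df, an apparent fall.

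For ρ between 0 and 1 the planned comparison errs upward by at most df. The eligible-only comparison errs toward showing suppression.

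**The case against.** The strongest reply is that the definition may be complete elsewhere. Table 2 points to the Analysis Set Definition Document, which may already exclude these subjects. That stands, and it means one cannot say that failures were in fact retained, only that the SAP text retains them. It does not remove the need for a same-subjects summary. Protocol 8.12.1 also omits the Visit 2 test for subjects who withdraw before completing the open-label phase, so the two means can differ in composition in any case.

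It is also fair that the output is descriptive: SAP 5.5.7 plans no change score, test or paired comparison. A failure on the pre-stimulation limit alone may have a normal 30-minute value and would lower the time-0 mean instead. Broad exposed-subject sets are usual for safety.

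Three stronger readings are tempting, and the documents do not support them.

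- A reader might infer that on-treatment suppression counts are distorted. They are not if 8.12.1 is followed, because failures have no result at Visits 2, 8 or 15. The maintenance tables show no Visit 1 data, so at most a column n is inflated.
- Because the SAP's open-label phase runs "From the day of enrolment to the day before randomisation", a reader might infer that pre-drug low values cannot be told from suppression by the drug. Shell 95 labels each individual value by visit and sample time, and Shell 96 has separate Visit 1 and Visit 2 blocks.
- A reader might infer that suppression percentages are diluted. That needs the header n as denominator, which the SAP does not state. Shell 96 has a Total row in each block, and protocol 11.3.8 sets observed cases by visit. That rule refers to visit attendance, however, and a failure can attend Visit 2 without an ACTH test, so the denominator is worth stating.

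**Conclusion.** The point holds for the open-label HPA set as Table 2 is written, and for the Visit 1 and Visit 2 means in Shell 94 and Figure 3-1. Those means can rest on different subjects, and the loss of low responders pushes the apparent change upward and can partly mask a fall. The documents give no failure rate and no cortisol distribution, so the actual size is unknown. The illustrated 0.14 to 1.25 mcg/dl depends on the assumed k, N and d and is an upper limit before regression to the mean. The conclusion also assumes that failures were dosed in the main trial and that the unsupplied document does not exclude them. The matter is minor: it concerns the clarity and comparability of a descriptive safety summary.

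**What to change.** In SAP 5.2 and 5.5.7:

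- Present the Visit 1 against Visit 2 cortisol summary and mean plot (Shell 94, Figure 3-1) in subjects who met criterion 13 and were tested at both visits.
- State that percentages at or below 18 mcg/dl use the subjects tested at that visit as denominator.
- Report criterion-13 failures as a separate count.
- Keep the Visit 1 rows and the individual data by visit (Shells 95 and 96), since they disclose baseline status.
- If the Analysis Set Definition Document already excludes these subjects, say so in Table 2.
- Note in the report that selecting on more than 18 mcg/dl at Visit 1 brings some regression to the mean, which errs toward showing suppression.

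The cost is SAP wording and table programming. No new data are needed.

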5.3 Baseline Considerations

5.3.1 Baseline definition

As described in the protocol, baseline is defined as the measurement taken at screening or visit 1.

The maintenance phase baseline is defined as the last available measurement collected at randomisation (visit 2).

Baseline for rebounds will be handled differently as described in section [5.5.4](#).

5.3.2 Disposition of subjects

The reason for leaving the trial will be presented as described in the protocol.

In addition, cumulative incidence plots of discontinuation by reason for withdrawal will be done for subjects leaving the trial during the open-label phase or the maintenance phase, respectively. The plots for the maintenance phase will be presented by treatment group.

Further details for the tables can be found in [Appendix I](#) and [Appendix II](#).

5.3.3 Demographics

Demographics and other baseline characteristics will be presented as described in the protocol. Age groups (18-64, ≥ 65) will also be presented for all enrolled subjects and for all randomised subjects by treatment group.

More details for tables for demographics and other baseline characteristics are given in [Appendix I](#) and [Appendix II](#).

Trial ID: LP0053-1004	Date: 15-JUL-2019	Version: 1.0 Page 10 of 177
-----------------------	-------------------	--------------------------------

5.3.4 Compliance

For the open-label treatment phase, number of subjects in non-compliance with treatment instructions together with percentage of missed daily applications of IMP will be summarised for the open-label safety analysis set.

For the maintenance phase, number of subjects in non-compliance with maintenance treatment instructions (i.e.; excluding relapse periods) will be summarised by treatment group both for each visit interval and for the total maintenance phase for the safety analysis set. The compliance information will be assigned to the visit interval by collection date.

For the relapse periods, number of subjects in non-compliance with rescue treatment instructions and percentage of missed daily applications of rescue IMP will be summarised by treatment group for the safety analysis set.

For an overview of changes as compared to the protocol refer to section [5.7](#).

5.4 Analysis of Efficacy

The assessment of efficacy is done for the maintenance phase. The primary and secondary efficacy endpoints will be analysed for the full analysis set, with the analyses for the per protocol analysis set being supportive. Sensitivity analyses are done for the full analysis set. Trial sites will be pooled as described in section [5.6.4](#) and will be referred as pooled sites.

5.4.1 Primary Efficacy Endpoint

The primary endpoint will be analysed using a cox proportional hazards model with treatment group, pooled sites, and disease severity at maintenance baseline (as determined by the PGA) as factors. Maintenance baseline is used in the model as compared to baseline at visit 1. See section [5.7](#) for details regarding changes as compared to the protocol.

The survival curves will be estimated using the Kaplan-Meier estimator. A log-log transformation will be applied to the survival function to obtain the pointwise confidence intervals in addition to the confidence intervals for the percentiles of the estimated survival times. The estimated survival curves and the confidence limits will be shown graphically. The percentiles of the estimated survival distribution and 95% confidence limits for the percentiles will be tabulated by treatment group.

Number of subjects still at risk of first relapse at timepoints for scheduled visits will be summarised by treatment group.

Further details for tables, figures and listings for the primary endpoint are given in [Appendix I](#) and [Appendix II](#).

Sensitivity analysis:

In the sensitivity analysis the primary endpoint will be analysed incorporating interval censoring. We will consider three different types of censoring. Subjects who do not encounter a relapse during the trial and subjects who are withdrawn from the trial in the maintenance phase before having a relapse will be right-censored, and the number of days will be treated as a censored observation at the end date of the maintenance phase. Subjects who are confirmed to have a relapse at a scheduled visit are interval censored, and it is assumed that the start of the relapse is between the scheduled visit where the relapse is confirmed and the previous visit where PGA was measured for the subject. For subjects who are confirmed to have a relapse at an unscheduled visit, it is assumed that the relapse starts on the day of this visit. These subjects are assumed to have exact observations. More details are given in [Table 3](#).

The number of subjects without relapse, the number of subjects with relapse confirmed at a scheduled visit, and the number of subjects with relapse confirmed at an unscheduled visit will be summarised by treatment group.

Table 3: Censoring in the sensitivity analysis of primary endpoint

Relapse information	Censoring type	Observation type	Lower endpoint	Upper endpoint
No relapse	Right-censored	(x, .], where x is the day the subject completed the trial or withdrew from the trial, and . denotes that this is left missing	x	. (missing)
Relapse confirmed at scheduled visit	Interval censored	(x, y], where x is the day of the previous visit in which PGA was measured, without relapse, and y is the day of the visit, where relapse is confirmed	x	y
Relapse confirmed at unscheduled visit	Exact observation	[x, x], where x is the day of the visit where relapse is confirmed	x	x

Trial ID: LP0053-1004	Date: 15-JUL-2019	Version: 1.0 Page 12 of 177
-----------------------	-------------------	--------------------------------

In the sensitivity analysis, time to first relapse during the maintenance phase will be analysed using a proportional hazards model with treatment group, pooled sites, and disease severity at maintenance baseline (determined by the PGA) as factors. The model will incorporate interval censoring. The baseline hazard function is assumed to be a piecewise constant function within ten disjoint intervals. The ten intervals split the time axis such that each interval contains approximately equal number of unique boundary values and imputed middle points. The estimate of the hazard ratio of active treatment group relative to vehicle group together with the 95% confidence interval and p-value will be presented.

Furthermore, survival curves will be estimated using a non-parametric maximum likelihood estimator, namely the Turnbull self-consistency algorithm. Standard errors will be computed using multiple imputation with 1000 samples (seed=39506291). A log-log transformation will be applied to the survival function to obtain the pointwise confidence intervals in addition to the confidence intervals for the percentiles of the estimated survival times. The estimated survival curves and the confidence limits will be shown graphically. The percentiles of the estimated survival distribution and 95% confidence limits for the percentiles will be tabulated by treatment group.

This sensitivity analysis was not specified in the protocol. See section [5.7](#) for details regarding changes as compared to the protocol.

Further details for tables, figures and listings for the sensitivity analysis are given in [Appendix I](#) and [Appendix II](#).

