6.1.3 Initial open-label treatment phase

Eligible subjects will first enter an initial open-label treatment phase, where they will be instructed to apply LEO 90100 once daily on the psoriatic lesions on trunk and limbs for 4 weeks. All trial medication needed for 4 weeks (7 cans of LEO 90100) will be dispensed at Visit 1.

The first application of the trial medication should be made at Visit 1 under the supervision and instruction of the trial staff or at home on the same day the subject attended Visit 1. For detailed treatment instructions, see section 10.2.

After 4 weeks, subjects will be asked to return to the trial site for clinical evaluation and medication accountability (Visit 2). All trial medication dispensed at Visit 1 will be collected.

Subjects who achieve treatment success (PGA score of 'clear' or 'almost clear' with at least a 2-grade improvement from baseline) at Visit 2 will be randomised in a ratio of 1:1 in a double-blind fashion to either LEO 90100 or vehicle (maintenance IP) twice weekly for 52 weeks.

The randomisation of subjects will be stratified by trial site, HPA axis testing, and by baseline disease severity, as determined by the PGA at Visit 1.

Randomised subjects will receive the supply of maintenance IP for 4 weeks and will be instructed on how to apply it during the maintenance phase and what to do in case of relapse.

Subjects who do not achieve treatment success after this initial open-label treatment phase will exit the trial.

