6.3 Randomisation

Subjects will be randomised in a 1:1 ratio to receive LEO 90100 or vehicle twice weekly during the maintenance phase. Randomisation will be stratified by trial site, HPA axis testing, and by baseline disease severity (mild, moderate, severe).

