11.3.3.3 Analysis of Primary Efficacy Endpoint

The primary endpoint is time to first relapse during the maintenance phase, where relapse is an exacerbation of psoriasis defined as a PGA of at least 'mild'. This will be calculated as the number of days from randomisation to the day where the subject has the first relapse confirmed. For subjects who either do not encounter a relapse or are withdrawn from the trial, the number of days will be treated as a censored observation at the day of end of trial visit.

The number of censored and uncensored observations, i.e. number of subjects without relapse or who are withdrawn from the trial, and number of subjects with relapse, will be summarised by treatment group. The time to first relapse will be summarised by treatment group for uncensored observations, i.e. subjects with relapse.

The primary endpoint will be compared between treatments with the null hypothesis that they are equal against the alternative that they are different. The analysis will be performed both for the full analysis set (primary) and for the per protocol analysis set (supportive). The comparison will be done using a proportional hazards model with treatment group, trial site, and disease severity at baseline (as determined by the PGA) as factors. The estimate of the hazard ratio of active treatment group relative to vehicle group together with the 95% confidence interval and p-value will be presented.

The estimated survival curves with confidence intervals will be presented graphically for each of the treatment groups. Moreover the percentiles of the survival distribution will be tabulated by treatment group.

The proportion of subjects who are still at risk for a first relapse will be compared between the two treatment groups at 26 and 52 weeks after randomisation.

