11.3.8 General Principles

All significance tests will be two-sided using the 5% significance level. All confidence intervals will be presented with 95% degree of confidence.

An observed cases approach will be used for tabulations of data by visit (i.e. involving only those subjects who attended each specific visit).

Categorical data will be summarised using the number and percentage of subjects in each category and treatment group. Continuous data will be summarised using the mean, median, standard deviation (SD), minimum and maximum values.

All the analyses specified in the protocol will be reviewed in relation to the blinded data actually obtained and the statistical analysis plan update will be finalised before breaking the randomisation code.

The randomisation is stratified by treatment group, trial site, HPA axis testing and disease severity at baseline as factors. Usually, the statistical analysis of efficacy parameters takes all the stratification factors into account. However, the HPA axis test is a safety parameter, which is only determined at a small subset of sites and subjects. Hence stratification by HPA axis test is not applicable for all sites. Also, it is expected that two subjects per site will be randomised. This means that a statistical model having HPA axis testing as a factor may not converge, depending on whether subjects participating in the HPA axis test drop out. Furthermore, the inclusion criteria for participating in the HPA axis test are “Moderate” or “Severe” in the baseline PGA assessment and a baseline BSA between 10 and 30%. Including the stratification factor HPA axis testing would therefore introduce a confounding with the

stratification according to baseline PGA as well as sites. Therefore the stratification according to HPA axis testing is not included in the statistical analyses.

Any changes from the statistical analysis planned in this clinical trial protocol will be described and justified in a protocol amendment/the statistical analysis plan update and/or in the clinical trial report dependent on the type of deviation.

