5.5.9	Laboratory Data	36
5.6	General Principles	37
5.6.1	Pooling of Trial Sites	37
5.6.2	Handling of Drop-outs and Missing Values	38
5.6.3	Incomplete dates	38
5.6.4	Multiplicity adjustment	38
5.6.5	Treatment Labels	39
5.7	Changes to the analyses described in the protocol	40
	Appendix I	47
	Appendix II	67

Trial ID: LP0053-1004	Date: 15-JUL-2019	Version: 1.0 Page 6 of 177
------------------------------	--------------------------	-------------------------------

3 List of Abbreviations

ACTH	Adrenocorticotropic Hormone
AE	Adverse Event
ATC	Anatomical Therapeutic Chemical
BSA	Body Surface Area
CPM	Clinical Project Manager
CPMP	Committee for Proprietary Medicinal Products
CRA	Clinical Research Associate
CRF	Case Report Form
CRO	Contract Research Organisation
DK	Denmark
DLQI	Dermatology Life Quality Index
eCRF	Electronic Case Report Form
eDiary	Electronic Diary
EU	European Union
GCP	Good Clinical Practice
ICH	International Conference on Harmonisation
IEC	Independent Ethics Committee
IMP	Investigational Product
IRB	Institutional Review Board
m-PASI	Modified Psoriasis Area Severity Index
MedDRA	Medical Dictionary for Regulatory Activities
MMRM	Mixed effect Model Repeat Measurement
ML	Maximum Likelihood
PASI	Psoriasis Area Severity Index
PASI 75	A 75% reduction in the modified Psoriasis Area Severity Index
PGA	Physician's Global Assessment of Disease Severity
PRO	Patient Reported Outcome
PSI	Psoriasis Symptom Inventory
REML	Restricted Maximum Likelihood
SAE	Serious Adverse Event

SAP	Statistical Analysis Plan
SD	Standard Deviation
SGA	Subject's global assessment of disease severity
SOC	System Organ Class
SOP	Standard Operating Procedure
UNS	Unscheduled Visit

4 Introduction

The statistical analysis will be performed as outlined in the Clinical Trial Protocol including amendments. This statistical analysis plan, prepared before the unblinding of the trial, but after the blind review of the data, contains a more technical and detailed elaboration of some points in the statistical analysis described in the Clinical Trial Protocol. Deviations from the planned data presentation and analysis are also described in section [5.7](#). Furthermore, the analysis sets, which are to be used for the statistical analysis, are presented.

5 Statistical Analysis

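### The SAP drops Visit 1 PGA, a stratification factor, from the primary and relapse-count models without a stated reason, and gives the days-in-remission ANOVA two different severity covariates

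*SAP*

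**What the plan says.** Protocol 6.1.3 stratifies randomisation by site, HPA axis testing and "by baseline disease severity, as determined by the PGA at Visit 1". Sections 6.3 and 10.6 repeat this with three grades: mild, moderate and severe. The primary analysis in protocol 11.3.3.3 is a "proportional hazards model with treatment group, trial site, and disease severity at baseline (as determined by the PGA) as factors". Sections 11.3.3.5 (days in remission) and 11.3.3.6 (number of relapses) also adjust for baseline severity. Section 11.3.8 explains why HPA axis testing is left out of the models and makes no such argument for severity. It asks that changes be "described and justified in a protocol amendment/the statistical analysis plan update and/or in the clinical trial report".

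The SAP was "prepared before the unblinding of the trial, but after the blind review of the data" (Section 4). In 5.4.1 it says "Maintenance baseline is used in the model as compared to baseline at visit 1". The interval-censored sensitivity analysis is likewise a "proportional hazards model with treatment group, pooled sites, and disease severity at maintenance baseline (determined by the PGA) as factors". Section 5.4.2.2 makes the same change in the Poisson and negative binomial models. For proportion of days in remission, 5.4.2.1 refers to the ANOVA of protocol 11.3.3.5, but Shell 27 describes the same analysis with severity at maintenance baseline, which is Visit 2 by SAP 5.3.1.

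**The concern.** There are two separate issues.

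- **A stratification factor leaves the models.** Sections 5.4.1 and 5.4.2.2 send the reader to 5.7 for details, but 5.7 only restates the swap. If Visit 1 PGA predicts relapse beyond what Visit 2 PGA captures, omitting it pulls the hazard ratio slightly towards 1 and loses some power.
- **An alpha-controlled endpoint has two stated models.** SAP 5.6.4 tests days in remission at 2.5% once the primary endpoint is significant. Two admissible ANOVAs mean two possible p-values for that test.

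**Working it through.** **1. The severity covariate, place by place**

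| Analysis | Protocol | SAP text | SAP 5.7 | Shell |
|---|---|---|---|---|
| Time to first relapse, Cox | Visit 1 (11.3.3.3) | Visit 2 (5.4.1) | swap stated, no reason | 23: Visit 2 |
| Same, interval-censored | not planned | Visit 2 (5.4.1) | analysis added | 23: Visit 2 |
| Number of relapses, Poisson | Visit 1 (11.3.3.6) | Visit 2 (5.4.2.2) | swap stated, no reason | 29: Visit 2 |
| Same, negative binomial | not planned | Visit 2 (5.4.2.2) | analysis added | 29: Visit 2 |
| Days in remission, ANOVA | Visit 1 (11.3.3.5) | by reference to 11.3.3.5, so Visit 1 (5.4.2.1) | endpoint and imputation only | 27: Visit 2 |

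Reading protocol baseline severity as Visit 1 is the SAP's own interpretation, in 5.7. Section 5.4.2.1 does say that the analysis differs from the protocol and points to 5.7. But that 5.7 row lists no covariate change, and it cites protocol 11.3.3.6, the number-of-relapses section. The site term is not in conflict, because SAP 5.4 says sites are pooled.

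**2. Visit 2 PGA is not a proxy for the stratum.** SAP 5.2 limits the full analysis set to subjects who are clear (0) or almost clear (1) with at least a 2-grade improvement. Mild is 2, and 2 − 2 = 0, so every mild subject must be clear. Moderate (3) and severe (4) subjects can be either, so Visit 2 PGA does not separate them.

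**3. The plan's own sample size reproduces.** Events needed = 4(1.960 + 1.282)²/(ln 0.7)² ≈ 331. The drop-out hazard is −ln(0.7)/52 = 0.00686 per week. The probability of an event is h/(h+d) × (1 − exp(−52(h+d))), averaged over arms: 0.878 at 4 relapses per year and 0.947 at 8. Schoenfeld's formula gives 175 to 189 per group and a numerical log-rank calculation gives 177 to 190. The protocol states 178 to 190. This calculation uses no covariates, so the figure stands whichever model is chosen. SAP Table 8 gives 132 + 55 + 52 + 68 + 56 + 68 + 114 = 545 randomised, with power of about 97% to 98% under the same assumptions.

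**4. Cox model simulation** (2,000 trials in each of 64 scenarios). From the documents: 1:1 allocation, 52 weeks, 30% drop-out, vehicle hazard 0.115 per week. Assumed: 10/70/20% mild/moderate/severe; 100/30/15% of these clear at Visit 2; each Visit 1 grade multiplies the hazard by 1.0 to 1.65; almost clear versus clear multiplies it by 1.0 to 2.0; site not modelled. Gain in power, in percentage points, of both PGAs over Visit 2 PGA alone (Monte Carlo SE at most 0.6):

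| Residual Visit 1 effect | N | HR 0.70 | HR 0.75 |
|---|---|---|---|
| none | 380 | −0.2 to 0.3 | −0.1 to 0.3 |
| none | 545 | −0.2 to 0.2 | −0.4 to 0.5 |
| 1.22 to 1.65 per grade | 380 | −0.3 to 2.5 | 0.3 to 3.6 |
| 1.22 to 1.65 per grade | 545 | 0.0 to 0.9 | 0.0 to 2.7 |

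- Mean HR at N=380 when the truth is 0.70 and a residual effect exists: 0.699 to 0.709 with Visit 2 PGA only, 0.694 to 0.699 with both.
- Type I error (8 null scenarios of 10,000 trials): SAP model 4.5% to 5.4%, protocol model 5.1% to 5.4%, both PGAs 5.0% to 5.6%.
- The swap alone, SAP minus protocol power: −0.2 to +5.2 points with no residual Visit 1 effect, −3.8 to +5.4 otherwise.

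A second simulation used other assumptions: 15/70/15% mix, 15% of moderate and 10% of severe clear at Visit 2, multiplier 1.5 for almost clear, N=380, true HR 0.70. At per-grade multipliers of 1.0, 1.5, 2.0 and 3.0 the model with Visit 2 PGA only gave HR 0.697, 0.707, 0.713 and 0.727. The model with both stayed at 0.696 to 0.700.

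**5. Days in remission** (2,000 trials in each of 42 scenarios). Set up with 364 days, 28-day relapse periods and the imputation of SAP 5.4.2.1 (100 imputations, Rubin's rule). Assumed: frailty SD 0.5; 15% withdrawal by subject or loss to follow-up over 52 weeks; 5% exit after each relapse treatment. Percentage of trials in which the Visit 1 and Visit 2 ANOVAs fall on opposite sides of p = 0.025 (Monte Carlo SE at most 0.8 points):

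| Rate ratio | N=380 | N=545 |
|---|---|---|
| 0.70 | 0.3 to 4.2 | 0.1 to 0.8 |
| 0.80 | 1.1 to 12.8 | 0.7 to 10.4 |
| 0.85 | 0.9 to 11.6 | 0.9 to 12.2 |

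The low ends occur when neither PGA is prognostic or both are only weakly so. The protocol plans on 0.70; the other two values are illustrative. An ANOVA with both PGAs has power −0.4 to +2.5 points relative to the better single-PGA model.

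**The case against.** The swap is disclosed, was fixed before unblinding and uses a valid pre-randomisation covariate. Efficacy is assessed in the maintenance phase, so the motive for a maintenance baseline can be guessed. Protocol 11.3.8 says only that analyses usually include all stratification factors, and it allows the justification to appear in the trial report. At 545 randomised and HR 0.70, adding Visit 1 PGA gains at most 0.9 points, and the swap by itself may well have helped. The prognostic strengths are all assumed. Shell 27 agrees with the SAP's other models, so the ANOVA conflict may be a slip in wording. Using both PGAs is a model that neither document contains.

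Most of this stands. The missing reason is not a breach of the protocol, and little power is at stake. What remains is that nothing in the SAP settles which ANOVA is confirmatory: text and shell disagree, and 5.7 is silent on the covariate. The two-PGA model is new, but it keeps both the design's stratum and the sponsor's chosen covariate, and no scenario showed a material cost. One further caveat is that the disagreement rates assume a fixed 2.5% level. SAP 5.6.4 also names Holm-Bonferroni, under which days in remission could be tested at 5% if number of relapses is rejected first.

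**Conclusion.** The concern holds on both counts. It should be acted on, but it does not threaten the trial's validity.

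- **Cox and count models:** restoring Visit 1 PGA is a nearly free improvement. In the Cox simulations it is worth 0 to about 3.6 points of power at N=380 and at most 2.7 at N=545, and it removes a slight attenuation of the hazard ratio. The gain depends on Visit 1 PGA predicting relapse given Visit 2 PGA, which the documents do not say. The count models were not simulated separately. Whether the SAP's swap is better or worse than the protocol model is unknown.
- **Days in remission:** the conflict is a matter of text and needs no assumption. Its consequence is rare at the planned effect (at most 4.2% of trials at N=380 and 0.8% at N=545) and could reach about one trial in eight at smaller effects with strongly prognostic PGA.

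**What to change.** Before unblinding:

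- Include Visit 1 PGA (three levels) as a factor alongside maintenance-baseline PGA in the Cox model, its interval-censored version, the Poisson and negative binomial models, and the days-in-remission ANOVA.
- State that one ANOVA, with pooled sites, in SAP 5.4.2.1, in 5.7 and in Shell 27. Align Shells 23 and 29 with the revised models.
- In 5.7, give the reason for adding maintenance-baseline PGA, and correct the days-in-remission references from protocol 11.3.3.6 to 11.3.3.5.

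The cost is two degrees of freedom per model and edits to the SAP and shells. The data are already collected.
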